2 STATISTICAL HYPOTHESES

Since the main objective of this study is to provide proof of concept for the efficacy of UCB0599 in reducing disease progression in study participants with early-stage PD, the null hypothesis for all efficacy analyses is that there is no difference between UCB0599 high dose and placebo.

This is an exploratory study with only one primary estimand (efficacy), therefore no formal multiplicity adjustments are planned. P-values from any statistical models will be presented but they should not be over-interpreted; any decision-making and interpretation should take the context of the analysis, the effect size and the confidence intervals into account (Wasserstein, 2016).

3 SAMPLE SIZE DETERMINATION

The sample size for this study was determined based on the primary efficacy estimand as detailed in the sections below. Approximately 645 participants will be screened to achieve 450 participants randomly assigned to study medication and 429 evaluable participants, for an estimated total of 143 evaluable participants per treatment group. Participants who terminate the study (withdraw consent) or are lost to follow-up will not be replaced.

The primary comparison of interest is UCB0599 high dose (360mg/day) vs placebo. Given the limitations in our understanding of the PK/PD properties of the compound, the sample size calculations presented below apply to both comparisons (UCB0599 high dose [360mg/day] and placebo and UCB0599 low dose [180mg/day] and placebo) as similar assumptions for both doses are made with respect to variability and impact on progression.

3.1 Primary efficacy estimand

The primary efficacy objective of PD0053 is to show superiority of UCB0599 over placebo with regards to clinical symptoms of disease progression over 12 months in participants diagnosed with early-stage PD. To measure clinical symptoms of disease progression, the MDS-UPDRS Part I-III sum score was selected as the variable of interest for the primary estimand and the population-level summary was chosen as the difference in the population mean slope of progression between UCB0599 and Placebo up to 12 months or up to the time of ST initiation, whichever comes first.

Even though the duration of the study is 18 months, the sample size was estimated to ensure 90% power at 12 months, where the proportion of participants who have initiated ST is still limited. Beyond 12 months, the number of participants under ST is expected to increase with significant potential for bias between the UCB0599 and placebo groups (should the compound be active), and power decrease due to data loss. The primary analysis of MDS-UPDRS is therefore planned at 12 months, and additional analyses will be performed at 18 months including post-ST initiation data in the analysis.

In order to derive the parameters of interest for sample size estimation, an Estimator similar to the one planned for the primary estimand (a linear mixed effects model (LMEM) for longitudinal data/repeated measures, with time as a continuous fixed effect, ie, assuming linear development over 12 months, and identical random effects to account for within-participant correlation between repeated observations – see [Section 5.3.1](#)) was applied to a subset of the Parkinson Progression Markers Initiative (PPMI) 1.0 de novo cohort, an observational study of early-stage PD participants (Parkinson's Progression Markers Initiative, 2018). The model was not adjusted for Baseline covariates.

Only patients enrolled in the early PD cohort from which participants with scan without evidence for dopaminergic deficit (SWEDD) were excluded, who were aged between 40 and 80 and who had been diagnosed with the disease for at most two years at screening were included in this analysis. This age range is larger than the one chosen for the study inclusion criteria (40 to 75 years), but since the variability is likely to be larger for those aged between 75 and 80, this approach is conservative. In addition, the following patients were also excluded:

- (1) patients for whom MDS-UPDRS at Baseline was not available;
- (2) patients who were already on ST at 3 months;
- (3) patients who had their MDS-UPDRS measured twice or less over the first 12 months of the study.

This left 361 out of the 423 early-stage PD participants in the dataset (participants with SWEDD excluded). This participant sample was assumed to be representative of the POC study placebo arm up to 12 months.

For the purpose of sample size estimation, a closed-form sample size formula for longitudinal data was used (Ahn, 2014 – Chapter 5, formula 5.19).

Number of participants per arm:

$$\frac{\left\{ \left(1 + \frac{1}{\lambda} \right) * \left(1 - \rho \right) + (r_\tau * N_1 * \text{Var}(T)) \right\} * Z_{(1-\frac{\alpha}{2}; \beta)}^2}{N_1 * \text{Var}(T) * \Delta^2}$$

Where λ is the allocation ratio, ρ is the intra-class correlation, r_τ is the ratio of the random slope variance component to the sum of the other variance terms (the random intercept variance component σ_u^2 and the residual variance σ_e^2), ie, $r_\tau = \sigma_{ut}^2 / \sigma^2$ with $\sigma^2 = \sigma_u^2 + \sigma_e^2$. N_1 is the number of timepoints, $\text{Var}(T)$ is the population variance of the timepoints and Δ is the absolute effect size standardized to σ (ie, $\Delta = (0.3 * \beta_t) / \sigma$, where β_t is the time coefficient from the LMEM applied to the PPMI data).

The causes for correlation can be modelled using random effects. The random effects will then induce the correlation structure of the marginal model. The formula used here assumes that the correlation between the participant-specific random intercept and the participant-specific random effect of time (random slope) is null and that $\sigma_{ut}^2 \approx 0$, resulting in a model equivalent to a random intercept model where intra-class correlation (ρ) $\approx \sigma_u^2 / \sigma^2$ for all participants and timepoints.

For the purpose of sample size calculation, the correlation between the random effects was set to 0 when running the LMEM. In practice, this correlation was estimated to be 0.43.

Therefore, in this case the resulting unconditional variance-covariance matrix resembles a compound symmetry working correlation matrix, ie, equivalent to a random intercept model with the variance of observations equaling σ^2 and covariance between observations equaling σ_u^2 .

In addition, the formula assumes the variance components will not differ by treatment group.

The frequency of MDS-UPDRS assessments was assigned to be bi-monthly. The population variance of the time points, $\text{Var}(T)$, was weighted for MDS-UPDRS data loss over time assuming an exponential loss function and a monotonic missing pattern.

All analyses were performed in R version 3.6.1 (2019-07-05, The R Foundation for Statistical Computing) using the lme4 package.

Based on the PPMI data, the parameters were estimated to be:

Table 3-1: Parameter estimates based on PPMI data

σ_u^2	154.0
σ_{ut}^2	0.43
σ_e^2	31.1
β_t	0.90
λ	1
$Z^2_{(1-\frac{\alpha}{2};\beta)}$	2.56 ²
N_1	7
$N_1 * \text{Var}(T)$	85.57 ^a

^a for 35% data loss at 12 months

3.2 Incorporating data loss

In the PPMI dataset, 10.7% of patients had a missing value recorded at their (initial) 3-month MDS-UPDRS assessment (42/391 patients aged 40-80 years), but only 3% (11/391) were truly lost to follow-up, see details below. Here, data loss cannot be explained by study termination related to study medication as no investigational treatment was applied. Another 2.6% of patients had initiated ST by 3 months (10/391).

A 5% data loss due to study termination by 3 months (all causes) will be assumed in this study, based on expert knowledge. The sample size will be inflated accordingly (see details below).

Loss to follow-up and loss to ST initiation by 3 months will be considered minimal in the study setting and will be ignored.

At 12 months, 58% (228/391) of the patients in the PPMI dataset had initiated ST (Figure 6-1 in Appendix 3, Section 6.3 illustrates this), and a least one missing value had been recorded at a single timepoint in 82% (320/391) of the patients. However, in the PPMI dataset missing data does not follow a monotonic missing pattern.

For example, out of the 32 patients who had a missing value recorded at 3 months, only 34% (11/32) had missing data for all 3 follow-up assessments up to 12 months, and 15% (5/32) had missing data on 2 follow-up assessments, while 41% (13/32) had only 1 further missing record, and 3 patients (10%) had valid records at 6, 9 and 12 months. Similarly, among the 27% (107/391) of patients who had a missing value recorded for the first time at 6 months, only 5% (5/107) of them had missing data for both 9 and 12 months follow-up, while among the 7% (27/391) of patients who had a missing value recorded for the first time at 9 months, 74% (20/27) of them had missing data at the 12-month follow-up. In addition, 9% (36/391) of patients had a first missing value recorded at 12 months, with 17% (6/36) of these having a missing value at 18 months (the presence of missing data was not investigated beyond 18 months for the purpose herewith).

If we assume that only those PPMI patients with a monotonic pattern of missing data would be representative of the missing data situation observed in a RCT setting, we would estimate another 10.7% (11+5+20+6 = 42/391) data loss at 12 months unrelated to initiation of ST ([Figure 6–1](#) in Appendix 3, [Section 6.3](#) illustrates this).

Based on these observations, 35% data loss was assumed in the study at 12 months:

3.3 Power for key secondary efficacy estimand (MDS-UPDRS Part III)

A key secondary estimand to the primary efficacy objective of PD0053 is the difference in population mean slope of progression between UCB0599 and placebo at 12 months in the absence of ST initiation for the MDS-UPDRS Part III subscale.

Using the same approach as described in [Section 3.1](#), the sample size estimated to achieve 90% power on the primary efficacy estimand (MDS-UPDRS Part I-III sum score) ie, 143 participants per arm, would provide 90% power to detect a minimum of expected 35% relative decrease in population mean slope of progression on the MDS-UPDRS Part III subscale (equivalent to 0.19 points/month or 2.3 points/year) in the UCB0599 treatment groups compared with placebo over 12 months of treatment, with 10% type I error (1-sided).

For the MDS-UPDRS Part III subscale, a decrease of 3.25 points mean change from baseline (95%CI -4.32; -2.17) has been identified as the minimal clinically important improvement (Horvath et al., 2015).

3.4 Power for secondary efficacy estimand (DaT-SPECT mean striatum SBR)

A secondary efficacy objective of PD0053 is to show superiority of UCB0599 over placebo with regards to neurodegeneration over 18 months in participants diagnosed with early-stage PD.

To assess neurodegeneration, the DaT-SPECT mean Striatum SBR was selected as a participant-level variable and the population-level summary chosen as the difference between UCB0599 and placebo in the population mean change from Baseline (screening) at 18 months.

Change from Baseline (screening) data was derived from the PPMI 1.0 de novo cohort DaT-SPECT mean Striatum SBR data. The same PPMI patients were selected as for MDS-UPDRS. In addition, patients for whom DaT-SPECT data was not available either at screening, 12 or 24 months were excluded from the analysis to derive the parameters of interest for sample size estimation. This left 297 out of the 423 early PD participants in the PPMI dataset.

As DaT-SPECT data was not available at 18 months in PPMI, we used the midpoint between the change from Baseline at 12 and 24-months as an estimate of the change from Baseline to be observed at 18 months. With respect to variability, we used the estimate of standard deviation for the 24-month data.

Using a two-sample t-test based sample size formula and the parameters for the placebo arm obtained from the PPMI 1.0 de novo DaT-SPECT data analysis, the sample size estimated to achieve 90% power on the primary efficacy estimand (MDS-UPDRS Part I-III sum score) ie, 143 participants per arm, would provide 90% power to detect a minimum of expected 37.5% relative increase in population mean change from Baseline in DaT-SPECT signal (equivalent to 0.067 SBR unit) in the UCB0599 groups vs placebo group at 18 months, with 10% type I error (1-sided), and assuming 25% data loss (ie, an extra 10% loss to occur between 12 and 18 months due to study termination and loss to follow-up at 18 months with effective N = 107/arm). Data loss due to ST initiation does not apply for the assessment of the DaT-SPECT signal as the assumption is being made that levodopa and dopamine agonists do not affect the neurodegeneration of dopamine neurons in the midbrain.

To increase information regarding DaT-SPECT SBR signal, participants intending to terminate the study (assumed to be 10% by 12 months) should have a scan before study termination (as part of the EOT visit). Participants who choose to withdraw from the study at or after 6 months and accept to have a scan at time of study termination will have their scan analysed as if it was taken at 12 months.

Residual data attrition due to study termination and loss to follow-up may be imbalanced between treatment arms by the time participants reach the 18-month timepoint, creating selection bias. This imbalance could happen in different directions depending on the balance of efficacy to AEs in the study. Compared to the placebo arm:

- a larger number of participants could be lost in the UCB0599 arms compared to placebo due to treatment-related AEs;
- a smaller number of participants could be lost in the UCB0599 arms compared to placebo due to treatment-related efficacy.

Consequently, different numbers and subtypes of participants per arm may continue to the end of the study. We estimate we would be left with an imbalance between arms of 5% due to data loss to follow-up, and another 5% data loss due to study termination before 6 months, as well as another 5% in the period between 12 and 18 months.

For these participants, we will control for bias at the analysis stage using implicit imputation of likelihood-based approaches (see [Section 5.3](#)).

4 POPULATIONS FOR ANALYSIS

The following analysis sets will be used:

- *All Study Participants Set (ASPS)*: All study participants who sign the ICF. Treatment assignment in the ASPS will be based on treatment received.
- *Randomized Set (RS)*: All study participants who are randomized. Treatment assignment in the RS will be based on treatment received.
- *Safety Set (SS)*: All randomized study participants who receive at least a partial dose of study medication. Treatment assignment in the SS will be based on treatment received.
- *Full Analysis Set (FAS)*: All randomized study participants who receive at least a partial dose of study medication, have at least 1 post-Baseline assessment. This is *any non-missing* post-baseline assessment, including unscheduled assessments. The FAS will be used for all efficacy analyses, and analyses will be conducted based on randomized treatment. This analysis set will exclude participants who do not meet key inclusion/exclusion criteria (see [appendix 6](#)), these will include criteria related to: age and disease duration at time of informed consent/baseline, Hoehn and Yahr stage at screening, evidence of dopamine transporter deficit (from screening DaT-SPECT) and ST status at screening.
- *Pharmacokinetic Set (PKS)*: All study participants in the Safety Set who have at least 1 observable PK measurement. The PKS will be used for PK analyses and treatment assignment in this analysis set will be based on actual treatment received.

The FAS will be used for all analyses with ICEs and other protocol deviations to be handled according to the approach specified for each estimand (see Sections 1.2). For a given endpoint, the analysis models will exclude any participant with a missing assessment at baseline for that particular endpoint.

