5.1.2.3 Treatment assignment and treatment groups

Participants will be randomized in a 1:1:1 ratio to receive either UCB0599 high dose (360mg/day), UCB0599 low dose (180mg/day) or placebo. All listings and summaries will be presented by treatment group unless stated otherwise. [Appendix 4](#) outlines which summaries should present an overall summary as well as data summarized by treatment group.

Table 5–2: Treatment group descriptions

Full Description	Data Display Label
Placebo	Placebo
UCB0599 360mg/day (180mg BID)	Minzasolmin 360mg/day
UCB0599 180mg/day (90mg BID)	Minzasolmin 180mg/day
UCB0599 pooled high dose (360mg/day) and low dose (180mg/day)	Minzasolmin Total

If after unblinding it is determined that participants received treatment other than what they were randomized to, then for baseline characteristics, safety and PK analyses participants will be allocated to the treatment they predominantly received (ASPS, RS, SS and PKS assignment will be based on actual treatment). Treatment assignment for the FAS will be allocated based on randomized treatment and not actual treatment received, all efficacy analyses will be based on the FAS. A sensitivity analysis will be performed for the primary estimand where actual treatment assignment is used.

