5.2 Participant dispositions

The number of study participants who started the study, completed the study, prematurely discontinued, and who enter the extension study will be presented by treatment group and overall. The reasons for discontinuation will also be summarized. This summary of disposition and discontinuation will be based on the RS. A study participant who completed the study is defined as a study participant who has a completed status in the study termination CRF. Since the primary estimand analysis in this study will be done using the first 12 months of data for each participant, the number of completers and the number of premature discontinuations will be summarized separately up to this time (in the same summary table). Participants who discontinue early are considered to have completed month 12 if their study termination date falls in or after the month 12 visit window.

The number and percentage of study participants who discontinue due to AEs will be summarized by treatment group, based on the RS. This summary will be used for European Union Drug Regulating Authorities Clinical Trials (EudraCT) reporting. This table will also present (separately) discontinuations due to AEs prior to the month 12 visit.

The number and percentage of study participants included in each of the analysis sets will be summarized by treatment group. Numbers will be presented for all analysis sets (including the ASPS) but percentages will be calculated based on the RS for the purpose of this summary. Additionally, a listing based on the SS will be produced for participants excluded from the FAS, including the reason for exclusion.

Screen failure reasons will be summarized for the ASPS. A separate summary will also be produced summarizing the reasons for ineligibility for those who screen fail due to being ineligible. A listing of study participants who did not meet study eligibility criteria will also be presented for this analysis set.

In addition, the following listings will be presented:

- Disposition of study participants (ASPS)
- Study discontinuation (RS)
- Visit dates (RS)
- Study participant analysis sets (ASPS)
- Rescreened Participants (ASPS)

The listing of disposition of study participants will include the date of informed consent, date of first and last dose of IMP, date of premature termination and primary reason (if applicable), date of final contact and whether the participant entered the extension study.

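### The SAP tabulates the Randomized Set by treatment received, so randomised but undosed participants have no stated arm in the per-arm disposition tables

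*SAP*

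**What the plan says.** SAP section 4 defines the RS by randomisation alone ("All study participants who are randomized") but assigns arms within it by what was taken: "Treatment assignment in the RS will be based on treatment received". The log for SAP Amendment 3 shows that assignment statements were added to every analysis set to guide output programming, so programmers can be expected to follow this one.

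Section 5.1.2.3 deals with participants found after unblinding to have been given something other than their randomised treatment. For baseline, safety and PK outputs, "participants will be allocated to the treatment they predominantly received", and a parenthesis adds that "ASPS, RS, SS and PKS assignment will be based on actual treatment". The FAS is the exception: "Treatment assignment for the FAS will be allocated based on randomized treatment and not actual treatment received".

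Section 5.2 then relies on the RS. The numbers who completed, "prematurely discontinued, and who enter the extension study will be presented by treatment group and overall". On the set used: "This summary of disposition and discontinuation will be based on the RS". On AE discontinuation: "The number and percentage of study participants who discontinue due to AEs will be summarized by treatment group, based on the RS". The analysis-set table also takes its percentages on the RS. Section 6.1.2 summarises important protocol deviations on the RS by arm and overall.

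Protocol section 9.1 attaches treatment received to the SS and randomised treatment to the FAS. It gives no assignment rule for the RS.

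**The concern.** The RS is the only set that holds everyone randomised, so its per-arm tables are where a reader looks for differential loss between the randomised groups. That matters here for two reasons. SAP section 3.4 itself expects that attrition may differ between arms and create selection bias. Section 4 and Appendix 6 remove participants from the FAS after randomisation if they fail key eligibility criteria, so the starting denominator in each arm needs to be the number randomised to it.

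A set defined by randomisation but labelled by receipt does not guarantee that denominator. Someone randomised and never dosed received nothing, and no rule places them in an arm.

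**Working it through.** The plan gives no figure to reproduce. The check is to follow two kinds of participant through the SAP's rules, then put illustrative counts on each.

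**Does the SAP expect randomised but undosed participants?** Yes. The AE-duration rules in section 5.1.1 (Table 5-1) name them, and section 6.1.1.1 allows for the RS and SS to differ. Protocol section 1.3 places the first dose on the evening of the Baseline visit, after randomisation, so the gap exists but is short.

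**Where would such a person appear?**
- Section 4, as written: no treatment received, hence no arm.
- Section 5.1.2.3: not triggered, because they did not receive a different treatment.
- Table 6-1 (Appendix 4): disposition has columns for not randomised, placebo, the UCB0599 arms and all participants. None is for randomised but not treated.
- The listing of FAS exclusions in section 5.2 is built on the SS, so they are not in it.
- The overall disposition column and the listings of disposition, discontinuation and analysis-set membership do include them.

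On that reading, each RS arm column holds the same people as the SS arm column, so the SS percentage of the RS is 100% in every arm by construction.

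**Never-dosed illustration.** Inputs: 450 planned, 150 per arm (protocol section 9.7.1). The never-dosed rate is an assumption, taken from 0% to 3%.
- Missing from the arm columns = 450 × rate. At 0% this is 0; at 2%, 9; at 3%, 13.5, or about 14.
- The arm columns then sum to between 450 and 436, while the overall column stays at 450.

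Early termination in one arm of 150, assuming 7 dosed participants stop early and k others are never dosed:
- As written: 7 / (150 − k).
- By randomised arm: (7 + k) / 150.
- k = 0: 7/150 = 4.7% on both.
- k = 2: 7/148 = 4.7% against 9/150 = 6.0%.
- k = 5: 7/145 = 4.8% against 12/150 = 8.0%.

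The as-written rate barely moves, because undosed participants leave both numerator and denominator.

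**Cross-over illustration.** Assume 150 per arm, all dosed and all in the FAS, with one placebo participant who predominantly received high dose.
- FAS by randomised arm: 150 and 150.
- RS by treatment received: 149 placebo, 151 high dose.
- FAS as a percentage of RS: 150/149 = 100.7% for placebo and 150/151 = 99.3% for high dose.

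The percentage above 100 shows that numerator and denominator follow different assignment rules.

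**The case against.** The best reply is that section 5.1.2.3 is the working rule and is narrower than section 4. It applies only when a different treatment was received, it names baseline, safety and PK outputs rather than disposition, and it moves only those who predominantly received the other treatment. On that reading an undosed participant simply stays in the randomised arm. Section 4 also applies treatment received to the set of all consented participants, which includes screen failures who took nothing, so the phrase may not be meant literally. Table 6-1 defers to the output shells, which are not among the documents and may already carry a suitable row.

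This limits the effect but does not settle the definition. Section 4 carries no condition, the parenthesis in 5.1.2.3 names the RS outright, and no section says where undosed participants go.

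Four stronger readings are tempting, and the documents do not support them:
- That the disposition table cannot show what happened to each randomised group. It can if everyone is dosed as randomised.
- That undosed participants vanish from the report. They stay in the overall disposition column and in the listings.
- That any dosing error moves a participant between arms. An isolated kit error moves nobody under the predominance rule.
- That the SAP contradicts the protocol. The protocol is silent on assignment in the RS.

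**Conclusion.** The point stands as a defect in a stated rule, confined to the per-arm tables built on the RS. If some participants are never dosed, per-arm attrition is understated as written: 4.7% against 6.0% in the illustration with 2 undosed. If some predominantly receive another arm's treatment, the FAS and RS counts for those arms no longer correspond. Both sizes rest on assumed counts, since the documents give no rate for either event, and dosing on the evening of the Baseline visit makes a large number of undosed participants unlikely. A reader might infer that the primary result is at risk. It is not: efficacy analyses use the FAS by randomised treatment, so no estimate, interval or p-value changes. The correction is worth making because it costs almost nothing and ensures that the arm columns add up to everyone randomised.

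**What to change.** - In SAP section 4, state that treatment assignment in the RS is the randomised treatment.
- In section 5.1.2.3, take the RS out of the parenthesis on actual treatment. Keep treatment received for the SS and PKS.
- In the disposition table, add a row for participants randomised but not dosed, shown by randomised arm.

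The cost is two phrases and one row in a table shell. SAP section 1 requires an amendment when analysis definitions change before database lock, so these edits would go into one. No data collection, efficacy analysis or sample size changes.
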